[Redacted contact information for Aerie Management and Sponsor Safety Officer]

Biostatistics and Data Management

AMENDMENT 1: 06 DECEMBER 2018

- Modified or added text:
 - [Synopsis](#) and Section 4.3 exclusion criteria number [14](#):
 - ADDED: Cannot demonstrate proper delivery of the eye drop, or in the investigator or co-investigator's opinion, unable to deliver the eye drop consistently.
 - Synopsis and Section 4.3 exclusion criteria number [20](#):
 - ADDED: Acceptable birth control includes: condoms plus intrauterine devices or condoms plus oral hormonal contraceptives, double barrier methods (e.g., condoms with spermicidal gel plus diaphragms). Birth control must be continued for at least 30 days after the last dose of the study drug.
 - Section [5.6](#)
 - WAS: Ocular or systemic medication known to cause corneal deposits or cornea verticillata, including but not limited to, indomethacin, ibuprofen, naproxen, amiodarone, chloroquine, hydroxychloroquine, mepacrine, tafenoquine, tamoxifen, and phenothiazine.
 - IS: Systemic medications known to cause corneal deposits or cornea verticillata including nonsteroidal anti-inflammatory drugs (NSAIDs), amiodarone, chlorpromazine, hydroxychloroquine, tamoxifen and phenothiazines.
 - ADDED: Subjects will be informed that benzalkonium chloride contained in this study drug as preservative agent has a risk to distain contact lenses.
 - Section [5.7.3](#)
 - ADDED: In addition, eye dilation may cause blurred vision and temporary sensitivity to light. While pupils are dilated, subjects should protect eyes while in bright light by wearing sunglasses. Subjects should not drive or engage in any hazardous activity until vision returns to normal.
 - Section [6.10.3](#)
 - ADDED: If the female partner of a subject become pregnant, the Investigator should collect information on the outcome of the pregnancy and the health of the baby (if applicable). The information will be reported to the sponsor to be used to understand the safety of the drug used during pregnancy.

SYNOPSIS

Sponsor: Aerie Pharmaceuticals Ireland Limited
Name of Finished Product: Netarsudil 0.01%, 0.02% and 0.04% Ophthalmic Solution
Name of Active Ingredients: Netarsudil
Study Title: A prospective, double-masked, randomized, multicenter, placebo-controlled, parallel-group study assessing the safety, ocular hypotensive efficacy and optimum dose concentration to be used clinically of netarsudil ophthalmic solution in subjects with open-angle glaucoma or ocular hypertension in Japan
Study Number: AR-13324-CS208
Study Phase: 2
Primary Objective(s): In this Phase 2 study, the primary objectives are to evaluate: 
• The ocular hypotensive efficacy of netarsudil ophthalmic solutions relative to placebo over a 28-day period• The ocular and systemic safety of netarsudil ophthalmic solutions relative to placebo over a 28-day period
Secondary Objective(s): None.
Study Design: 
This will be a prospective, double-masked, randomized, multicenter, placebo-controlled, parallel group efficacy and safety trial evaluating the intraocular pressure (IOP) lowering effect of 3 concentrations of netarsudil ophthalmic solution over a 28-day treatment period. The purpose of this study is to assess the efficacy and safety of netarsudil ophthalmic solution (0.01%, 0.02% and 0.04%) compared to placebo in subjects with open-angle glaucoma (OAG) or ocular hypertension (OHT) in Japan.
 
All investigational products will be dosed in both eyes (OU) once daily (QD) in the evening (PM). Subjects eligible to be enrolled in this study will be subjects with diagnosis of either OAG or OHT. Approximately 208 subjects will be enrolled in this study. Subjects who agree to participate in this study and are enrolled will attend a total of 6 study visits: Screening Visit, Qualification Visit #1, Qualification Visit #2/Day 1 (baseline), Week 1 (Day 8), Week 2 (Day 15), and Week 4 (Day 29).
 
Subjects will be required to washout of their pre-study ocular hypotensive medication for a prescribed period (i.e., 5 days to at least 6 weeks, depending on the medication) prior to attending Qualification Visit #1. Subjects eligible to be enrolled in this study must meet all inclusion criteria and none of the exclusion criteria at each of the Screening Visit and Qualification Visits #1 and #2. Subjects will receive a baseline eye examination including IOP measurements at the Screening Visit and Qualification Visits #1 and #2, and undergo additional testing at Qualification Visit #2 including National Eye Institute Visual Function Questionnaire (VFQ-25), Best Corrected Visual Acuity (BCVA), and Contrast Sensitivity (CS) testing. If deemed eligible, subjects will be enrolled at Qualification Visit #2 and assigned to placebo or 1 of 3 investigational products in a 1:1:1:1 ratio according to a computer-generated randomization list. Randomization will take place using Interactive Web Response System (IWRS) methodology and will stratify subjects by site.

Randomized subjects will dose the assigned investigational product in both eyes QD in the evening (between 20:00 and 22:00 hours) beginning on Day 1 and up to and including the evening prior to the final visit at Visit 6 (Week 4). Procedures conducted at each of study Visits 4-6 will include safety measures and efficacy measurements, including IOP assessments. At Visits 4-6 (Weeks 1, 2, and 4, respectively), IOP will be assessed at 09:00, 11:00 and 16:00 hours. Following completion of the Visit 6 (Week 4) study visit procedures, subjects will exit the study. For subjects who discontinue early, every possible effort will be made to assure there is a final visit that includes all examinations listed for Visit 6.0 (Week 4) and dilated ophthalmoscopy.

For subjects who show any evidence of cornea verticillata by slit lamp examination using the grading system for amiodarone keratopathy (Orlando, 1984) during the 28-day treatment period, the assigned investigational product will be discontinued, all examinations for exit visit (Visit 6) will be completed and subject will enter into an observational period to follow up and collect visual function data. Subjects will be evaluated at the time of discontinuation of study medication as OBS Visit 1 (Day 1), followed by monthly visits for 3 consecutive months (OBS Visit 2, 3 and 4). If cornea verticillata persists at OBS Visit 4, subjects will return every 2 months until resolution or stabilization. Resolution is defined as grading of zero of the cornea verticillata grading and stabilization is defined as no worsening of the cornea verticillata grading for a minimum of one year from the commencement of dosing. Procedures conducted at OBS visit 1 will include VFQ-25, BCVA, CS testing and cornea verticillata grading. If cornea verticillata persists, BCVA testing and cornea verticillata grading will be evaluated at each visit thereafter until resolution or stabilization of the cornea verticillata grading. Once resolution is recorded with cornea verticillata grading of zero or stabilization is confirmed in both eyes, the subject will undergo VFQ-25, BCVA testing, CS testing, and exit the study.

Inclusion Criteria:

Subjects have to meet all of the following criteria at screening and qualification visits to enter into the study:

1. Must be 20 years of age or older
2. Diagnosis of OAG or OHT in both eyes (OAG in one eye and OHT in the fellow eye is acceptable)
3. Medicated IOP ≥ 14 mmHg in at least one eye and < 30 mmHg in both eyes at screening visit (this also applies to treatment naive subjects)
4. For OAG eyes, unmedicated (post washout) IOP ≥ 15 mmHg and < 35 mmHg in the study eye at 2 qualification visits (09:00 hour), 2-7 days apart. At second qualification visit IOP ≥ 15 mmHg and < 35 mmHg at 11:00 and 16:00 hours (in the same eye). **Note: For purposes of determining eligibility of subjects to be enrolled, any non-integral mean IOP number should not be rounded**
5. For OHT eyes, unmedicated (post washout) IOP ≥ 22 mmHg and < 35 mmHg in the study eye at 2 qualification visits (09:00 hour), 2-7 days apart. At second qualification visit IOP ≥ 22 mmHg and < 35 mmHg at 11:00 and 16:00 hours (in the same eye). **Note: For purposes of determining eligibility of subjects to be enrolled, any non-integral mean IOP number should not be rounded**
6. BCVA 0.1 or better in decimal unit using Landolt-C chart or its equivalent (+ 1.0 logMAR or better by Early Treatment of Diabetic Retinopathy Study [ETDRS] or 20/200 or better by Snellen chart)
7. Be able and willing to give signed informed consent and follow study instructions

Exclusion Criteria:

Subjects meeting any of the following criteria during screening or qualification evaluations (e.g., at the time of randomization) will be excluded from entry into the study:

Ophthalmic:

1. Clinically significant ocular disease (e.g., corneal edema, uveitis, or severe keratoconjunctivitis sicca) which might interfere with interpretation of the study efficacy endpoints or with safety assessments, including subjects with glaucomatous damage so severe that washout of ocular hypotensive medications for up to 8 weeks is not judged safe as it would put the subject at risk for further vision loss

2. Pseudoexfoliation or pigment dispersion component glaucoma, history of angle closure glaucoma, or narrow angles (i.e., Shaffer Grade 2 or less). Note: Previous laser peripheral iridotomy is NOT acceptable
3. Ocular hyperemia score of moderate (+ 2) or severe (+3) at Qualification Visit #2
4. Previous glaucoma intraocular surgery, including selective laser trabeculoplasty (SLT) or argon laser trabeculoplasty (ALT) in the study eye
5. Refractive surgery in either eye (e.g., radial keratotomy, photorefractive keratectomy [PRK], laser-assisted in situ keratomileusis [LASIK], corneal cross-linking)
6. Ocular trauma within the 6 months prior to screening, or ocular surgery or non-refractive laser treatment within the 3 months prior to screening
7. Recent or current evidence of ocular infection or inflammation in either eye. Current evidence of clinically significant blepharitis, conjunctivitis, keratitis, or a history of herpes simplex or zoster keratitis in either eye at screening
8. Any corneal disease or condition in either eye that in the investigator opinion, may confound assessment of the cornea
9. Current evidence of corneal deposits or cornea verticillata in either eye
10. Use of ocular medication in either eye of any kind within 30 days of screening and throughout the study, with the exception of a) ocular hypotensive medications (which must be washed out according to the provided schedule), b) lid scrubs (which may be used prior to, but not after, screening), c) lubricating drops for dry eye (which may be used throughout the study), or d) non-steroid allergy drops (note: must not contain a vasoconstrictor) as prescribed by the Investigator
11. Mean central corneal thickness greater than 620 μm in either eye at screening
12. Any abnormality preventing reliable applanation tonometry of either eye (e.g., keratoconus)
13. Known hypersensitivity to benzalkonium chloride or excipients of netarsudil ophthalmic solution
14. Cannot demonstrate proper delivery of the eye drop, or in the investigator or co-investigator's opinion, unable to deliver the eye drop consistently

Systemic:

15. Current use of systemic medications known to cause corneal deposits or cornea verticillata including nonsteroidal anti-inflammatory drugs (NSAIDs), amiodarone, chlorpromazine, hydroxychloroquine, tamoxifen and phenothiazines
16. Clinically significant abnormalities in laboratory tests at screening
17. Clinically significant systemic disease which might interfere with the study
18. Participation in any investigational study within 30 days prior to screening
19. Systemic medication that could have a substantial effect on IOP within 30 days prior to screening, or anticipated during the study, including any corticosteroid-containing drug regardless of route of administration
20. Women of childbearing potential who are pregnant, nursing, planning a pregnancy, or not using a medically acceptable form of birth control. Acceptable birth control includes: condoms plus intrauterine devices or condoms plus oral hormonal contraceptives, double barrier methods (e.g., condoms with spermicidal gel plus diaphragms). Birth control must be continued for at least 30 days after the last dose of the study drug. An adult woman is considered to be of childbearing potential unless she is 1 year post-menopausal or 3 months post-surgical sterilization. All females of childbearing potential must have a negative urine pregnancy test result at the screening examination and must not intend to become pregnant during the study

Study Population:

A total of approximately 208 subjects will be enrolled in this study at approximately 30 investigational sites across Japan comprising a total of 52 subjects per treatment arm for each of the 4 treatment arms. Subjects

will be at least 20 years of age with diagnosed OAG or OHT, each of whom meets all inclusion criteria and none of the exclusion criteria.
Investigational Product, Dose, and Mode of Administration: 
• Netarsudil Ophthalmic Solution 0.01%, 1 drop QD (PM), OU• Netarsudil Ophthalmic Solution 0.02%, 1 drop QD (PM), OU• Netarsudil Ophthalmic Solution 0.04%, 1 drop QD (PM), OU• Netarsudil Ophthalmic Solution Placebo, 1 drop QD (PM), OU
Duration of Treatment: 
Dosing will continue daily for 28 days continuously.

Efficacy Assessments: 
The primary efficacy outcome will be the comparison of netarsudil ophthalmic solutions (0.01%, 0.02% and 0.04%) relative to placebo for mean diurnal IOP within a treatment at Week 4 (Day 29) by Goldmann Applanation Tonometry.
 
Secondary efficacy outcomes will be comparison of netarsudil ophthalmic solutions relative to placebo for:
 
• Mean diurnal IOP at Weeks 1 and 2 (Days 8 and 15, respectively)• Mean change from baseline in mean diurnal IOP at each post-treatment visit• Mean percent change from baseline in mean diurnal IOP at each post-treatment visit• Mean IOP at each post-treatment time point• Mean change from diurnally adjusted baseline IOP at each post-treatment time point• Mean percent change from diurnally adjusted baseline IOP at each post-treatment time point• Percentages of subjects achieving pre-specified mean, mean change, and percent mean change in mean diurnal IOP levels 
Other secondary efficacy analyses may be carried out as described in the study Statistical Analysis Plan.

Safety Assessments: 
Treatment Period:
 
Primary safety assessments:
 
• Ocular symptoms/adverse events• VFQ-25 at baseline• BCVA will be determined and completed prior to any IOP measurements• CS testing at baseline• Objective findings of biomicroscopic examinations (i.e., anterior segment examinations including evaluation of cornea, conjunctiva, lids, and lens)• Dilated ophthalmoscopy, including vertical cup-disc ratio measurements 
Additional safety assessments:
 
• Systemic safety assessments as measured by heart rate, blood pressure, and clinical laboratory evaluations (including hematology, clinical chemistry, and urinalysis)• Pregnancy testing (for women of child bearing potential) 
Observational Period (For subjects who develop cornea verticillata):
 
• VFQ-25• BCVA• CS testing• Cornea verticillata grading

- Time to cornea verticillata resolution or stabilization of cornea verticillata grading score

Statistical Methods:

The primary efficacy endpoint is the mean diurnal IOP (average of 09:00, 11:00, and 16:00 hours) at Week 4. Assuming a two-sided test with $\alpha = 0.05$, a common standard deviation (SD) of 3.5 mmHg at each time point yielding a common SD of 3.0 for the mean diurnal IOP, and a correlation among time points of 0.60, 49 ITT subjects per arm yields 90% power to demonstrate superiority for each concentration of netarsudil (0.01%, 0.02% or 0.04%) to placebo in study eye mean diurnal IOP at the Week 4 Visit assuming a difference of at least 2.0 mmHg in the mean diurnal IOP. The study will be considered a success and superiority of netarsudil to placebo will be concluded if the two-sided p-value is ≤ 0.05 at Week 4 for at least one concentration of netarsudil. Accounting for approximately a 5% discontinuation rate, 52 subjects per arm (208 total) will be enrolled.

The primary analysis of the primary outcome will employ a linear model with mean diurnal IOP at Week 4 as the response, baseline mean diurnal IOP as a covariate, and treatment as a main effect factor, using the intent to treat population with Monte Carlo Markov Chain multiple imputation techniques used to impute missing data. The least squares mean differences (netarsudil – placebo) will be presented separately for netarsudil 0.01%, 0.02% and 0.04% as well as 2-sided p-values and 95% confidence intervals (CIs). Inference will be made on the 2-sided p-values. Superiority for a concentration (0.01%, 0.02% and 0.04%) will be concluded if the 2-sided p-value, for testing the difference (netarsudil – placebo) to 0, is ≤ 0.05 and the point estimate of the difference is < 0 at Week 4 for that concentration.

There will be no adjustment for the multiplicity of the 3 active concentrations (0.01%, 0.02% and 0.04%) tested against placebo in this Phase 2 study.

In subjects who have cornea verticillata, CS and BCVA will be summarized at the eye level for the initial assessments and for follow-up visits as well as change from the initial assessment by treatment group and by whether or not the cornea verticillata event was ongoing at a given visit. The VFQ-25 scores will be summarized similarly at the subject level.

The grading of the cornea verticillata will be summarized at eye level for initial and follow-up visits in a similar manner to that described above for the visual function parameters.

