3.2 Rationale for Study Design and Control Group

In order to further evaluate the hypotensive efficacy of netarsudil ophthalmic solution relative to its placebo in subjects with OAG or OHT and to generate additional safety data for netarsudil in Japanese population, a double-masked, parallel group, 4-arm active- and placebo-controlled study design was selected.

As the intended route of administration for netarsudil ophthalmic solution is topical ocular, this is the route to be used in this study. The dosage regimen selected for this study is based on a previously completed Phase 2 study (AR-13324-CS201) and 4 completed Phase 3 studies (AR-13324-CS301, AR-13324-CS302, AR-13324-CS303, and AR-13324-CS304).

A Phase 1 study (AR-13324-CS104) evaluating the ocular and systemic safety of 2 concentrations of netarsudil (0.02% and 0.04%) ophthalmic solution compared to placebo over a 7-day period was conducted in healthy volunteers of Japanese ethnicity within the second generation in the United States. However, efficacy results with netarsudil ophthalmic solution to date have been generated in a mostly non-Japanese population. In order to ensure that similar results are observed in Japanese subjects, this study is being conducted in subjects in Japan.

The design of the observational period for subjects who develop cornea verticillata during the study is based on an observational study conducted in the United States in a non-Japanese population (AR-13324-OBS01). Per discussion at PMDA meeting, long term follow-up is necessary in order to understand the impact on visual function and resolution of cornea verticillata in Japanese population.

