6.7 Safety Assessments

The primary safety measures in both eyes of enrolled subjects will include:

- Ocular symptoms/adverse events
- VFQ-25 at baseline
- BCVA will be determined and completed prior to any IOP measurements.
- CS testing at baseline
- Objective findings of biomicroscopic examinations (i.e., anterior segment examinations including evaluation of cornea, conjunctiva, lids, and lens)
- Dilated ophthalmoscopy, including vertical cup-disc ratio measurements

Other safety assessments will be:

- Systemic safety assessments as measured by heart rate, blood pressure, and clinical laboratory evaluations (including hematology, clinical chemistry, and urinalysis)

For subjects who develop cornea verticillata, safety measures include:

- VFQ-25
- BCVA
- CS testing
- Cornea verticillata grading
- Time to cornea verticillata resolution

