6.12 National Eye Institute Visual Function Questionnaire (VFQ-25)

The VFQ-25 is a reliable and valid 25-item version of the 51-item National Eye Institute Visual Function Questionnaire that measures subjective assessment of patient-reported vision-targeted health status elements that are most important to people with eye disease. All subjects will undergo VFQ-25 at Visit 3. Subjects noted to have cornea verticillata will undergo additional VFQ-25 throughout the study. A Japanese version of the VFQ-25 will be used, the responses will be documented, and a score assigned. See MOPs for additional details.

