6.13 Contrast Sensitivity Testing

Contrast sensitivity charts will be used to assess visual function. All subjects will have a CS testing at Visit 3. Subjects noted to have cornea verticillata will undergo CS testing during the study. See MOPs for additional details.

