2.3 Safety Endpoints – Treatment Period

The safety endpoints include the following:

- Ocular symptoms/adverse events (AEs)
- Visual Function Questionnaire (VFQ-25) at baseline
- Best Corrected Visual Acuity (BCVA)
- Contrast Sensitivity (CS) testing at baseline
- Objective findings of biomicroscopic examinations (i.e., anterior segment examinations including evaluation of cornea, conjunctiva, lids, and lens)
- Dilated ophthalmoscopy, including vertical cup-disc ratio measurements

Systemic safety assessment will include:

- Vital signs (heart rate and blood pressure)
- Clinical laboratory evaluations (including hematology, clinical chemistry, and urinalysis)
- Pregnancy testing (for women of childbearing potential)

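### VFQ-25 and contrast sensitivity are listed as treatment-period safety measures, but only verticillata subjects are tested after dosing, so neither can be compared with placebo, and no planned analysis uses the Visit 3.0 values as a reference

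*Protocol*

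**What the plan says.** - **Objective.** One of the two primary objectives is to evaluate "The ocular and systemic safety of netarsudil ophthalmic solutions relative to placebo over a 28-day period" (Protocol Synopsis and 2.1; SAP 2 has the same objective).
- **Safety lists.** Under primary safety assessments for the treatment period, the Synopsis gives "VFQ-25 at baseline" and "CS testing at baseline". Protocol 6.7 repeats both under "The primary safety measures in both eyes of enrolled subjects will include". Protocol 9.7.1 and SAP 2.3 carry them as treatment-period safety endpoints; the SAP entry reads "Contrast Sensitivity (CS) testing at baseline".
- **Timing.** "All subjects will undergo VFQ-25 at Visit 3" (6.12) and "All subjects will have a CS testing at Visit 3" (6.13). Appendix 1 marks each test once, at Visit 3.0. The first dose follows that evening (7.3.3). Sections 7.3.4 to 7.3.12, covering Visits 4 to 6, contain neither test.
- **Later tests.** Only subjects with cornea verticillata are tested again, at OBS Visit 1 and the final observational visit (Protocol 7.4.1, 7.4.4; SAP 10.3, 10.4).
- **Analysis.** SAP 10.3 and 10.4 place both measures under demographic and pretreatment variables, and the treatment-period tables show them at baseline. For the observational period, SAP 16.1 takes VFQ-25 change from OBS Visit 1. SAP 16.3 summarises contrast sensitivity (CS) by visit and by whether the deposits are ongoing. Protocol 9.7.2 takes change from the initial observational assessment and adds change from the treatment-period baseline for visual acuity alone.
- **Reason for the observational period.** Protocol 3.2, citing a meeting with the regulator, says that "long term follow-up is necessary in order to understand the impact on visual function and resolution of cornea verticillata in Japanese population".

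**The concern.** A value recorded only before dosing cannot show an effect of the drug. Two measures listed as safety endpoints therefore contribute nothing to the comparison with placebo.

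Visual function matters in this programme. Protocol 1.3 reports blurred vision and reduced visual acuity in 5-10% of patients on the marketed 0.02% product, and Protocol 3.2 names the impact of verticillata on visual function as an open question for Japanese patients. A drug effect on contrast or on reported visual function in subjects without deposits would not be seen on these two instruments.

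The pre-dose values are also left unused where a post-dose value does exist. All 208 planned subjects supply a Visit 3.0 reading. In verticillata subjects, however, the planned reference is OBS Visit 1, when deposits are already present. The summaries then describe recovery after the drug is stopped, and do not describe how far function had moved from its pre-treatment level.

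**Working it through.** **1. Which values exist under the plan (Appendix 1; 7.3; 7.4)**

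| Subjects | Visit 3.0 (pre-dose) | Visits 4 to 6 | OBS Visit 1 | Final OBS visit |
|---|---|---|---|---|
| Placebo or netarsudil, no verticillata | VFQ-25, CS | none | not applicable | not applicable |
| Any arm, verticillata | VFQ-25, CS | none outside OBS Visit 1 | VFQ-25, CS | VFQ-25, CS |
| All arms, BCVA for comparison | yes | yes | yes, if verticillata | yes, if verticillata |

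A between-arm difference in change needs a post-dose value in the randomised arms. For VFQ-25 and CS it exists only in a subgroup defined by an event after randomisation, so the randomised difference is not estimable. This follows from the schedule and needs no assumption about event rates.

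**2. Which comparisons are planned in verticillata subjects**

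- VFQ-25: change from OBS Visit 1 (SAP 16.1).
- CS: change from the initial observational assessment (Protocol 9.7.2); SAP 16.3 states no change variable.
- BCVA: change from OBS Visit 1 and from the treatment-period baseline (Protocol 9.7.2; SAP Tables 14.4.5.1 and 14.4.5.2).

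The change from Visit 3.0 is therefore missing for VFQ-25 and CS only.

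**3. The plan's sample size, reproduced**

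The documents give no sample size for VFQ-25 or CS. The IOP calculation (Protocol 9.2) supplies the arm size.

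- SD of the mean of three readings = 3.5 × √((1 + 2 × 0.60)/3) = 2.997, stated as 3.0.
- Difference 2.0, SD 3.0, two-sided 0.05, 90% power: t-based n = 48.3, so 49 per arm. Power at 49 is 90.4%.
- Dropout: 49/0.95 = 51.6, so 52 per arm and 208 in total.

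These figures reproduce and are unaffected by this point.

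**4. Precision if everyone is tested at Visit 6.0**

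Half-width of the 95% CI, in SDs of change, unadjusted, n = 49 per arm:

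t(0.975, 96) × √(2/49) = 1.985 × 0.202 = 0.40 SD.

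The documents give no SD for either measure, so this cannot be converted to score points.

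**5. How many subjects would have a post-dose test as planned (illustration only)**

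Protocol 1.1 gives a once-daily verticillata rate of 16.7% (76/454), with first detection between 2 and 13 weeks. Applied to 3 × 52 = 156 netarsudil subjects: 156 × 0.167 = 26.

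| Assumed share of onsets by Week 4 | Cases | Of 208 with no post-dose test |
|---|---|---|
| 18%, onset uniform over weeks 2-13: (4 − 2)/(13 − 2) | 26 × 0.18 = 4.7, about 5 | 203/208 = 97.6% |
| 50%, assumed front-loaded | 13 | 195/208 = 93.8% |
| 100%, ceiling | 26 | 182/208 = 87.5% |

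The table also assumes no placebo cases and the same rate at all three concentrations. The documents give no placebo rate, and Protocol 1.1 calls the finding dose dependent.

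**6. Verticillata against verticillata-free netarsudil subjects (147 = 3 × 49)**

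- 5 against 142: 1.976 × √(1/5 + 1/142) = 0.90 SD.
- 13 against 134: 1.976 × √(1/13 + 1/134) = 0.57 SD.

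This comparison would be imprecise even with the added test.

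**The case against.** The strongest reply is that no planned analysis fails. Both entries say openly that the tests are done at baseline, no section plans a placebo comparison of either measure, and the SAP already handles them as pretreatment variables. That is correct. The link to placebo comes from reading the safety lists together with the primary objective. What remains is that measures listed as safety endpoints have no post-dose value in most subjects.

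A reader might infer more, and the documents do not support it:

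- **That ocular safety against placebo cannot be assessed.** Adverse events, BCVA, biomicroscopy and ophthalmoscopy are collected after dosing in every arm, and each adverse event is compared with placebo (Protocol 9.7.2; SAP 15.1). Blurred vision and reduced acuity would be captured there.
- **That the trial gives no information on the effect of deposits.** CS is summarised by whether the deposits are ongoing (SAP 16.3), and Protocol 9.7.2 plans VFQ-25 similarly. This is a within-subject contrast between deposits present and resolved. It is confounded with stopping the drug, but it exists.
- **That the planned analysis is a confounded change from Visit 3.0.** That change is not planned; its absence is part of the point.
- **That the regulator asked for a placebo-controlled VFQ-25 or CS comparison.** Protocol 3.2 speaks of long-term follow-up and asks for nothing of that kind.

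It is also fair to say that a Visit 6.0 test would not give a clean verticillata against verticillata-free comparison. Cases found at Visit 4 or 5 are tested on that day and the others at Day 29, the groups are formed after randomisation, and they are small. That objection stands and limits what the added test can be used for. It does not affect the comparison by randomised arm.

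**Conclusion.** The point holds as a missed, inexpensive gain and not as a failure of the safety objective. VFQ-25 and CS are listed as treatment-period safety measures, yet no netarsudil-placebo difference can be estimated for either. In verticillata subjects the pre-dose values are never used as the reference. Both statements rest on the schedule and analysis text alone.

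The supplied protocol is Amendment 1, while the SAP was written for Amendment 2; SAP 10.3 and 10.4 still describe the same timing. The Manual of Procedures was not available.

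With everyone tested at Visit 6.0, each active-placebo difference would have a 95% half-width of about 0.40 SD of change, assuming 49 evaluable subjects per arm. The estimate that about 88-98% of subjects would otherwise lack a post-dose test depends on assumed onset shares and no placebo cases, and is illustrative only.

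**What to change.** 1. **Add VFQ-25 and CS at Visit 6.0 for all randomised subjects**, in the same order as at Visit 3.0, in Protocol Appendix 1, 6.12, 6.13 and 7.3.10 and SAP 10.3 and 10.4. Where OBS Visit 1 already covers the tests, do not repeat them; carry those values into the arm comparison so that verticillata subjects are not dropped from it. Report change from Visit 3.0 by arm, with the difference from placebo and a 95% CI. Early leavers are already asked to complete Visit 6.0 procedures, so those who attend would be included.
2. **Use the existing Visit 3.0 values in verticillata subjects.** In SAP 16.1 and 16.3 and Protocol 9.7.2, add change from Visit 3.0 for VFQ-25 and CS, as is already planned for visual acuity.
3. **Label any verticillata against verticillata-free comparison as descriptive**, and give the reasons: groups defined after randomisation, possibly different test days, and small numbers.

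**Cost.** One questionnaire and one chart test per subject, at a visit that already runs from 09:00 to 16:00, using materials already needed for Visit 3.0. Visit 6 becomes slightly longer. The protocol change needs an amendment submitted to the IRBs and possibly a consent revision, across about 30 sites. Item 2 needs no new data.

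If the tests are not added, describe both measures as baseline reference values only in the Synopsis, Protocol 6.7 and 9.7.1 and SAP 2.3. That makes the text accurate but adds no information.
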